4.1.2.1. Screening

The following screening procedures must be performed within 28 days prior to the first day of study therapy unless indicated. Qualifying hematology, serum chemistry (including thyroid-stimulating hormone [TSH] testing), coagulation, physical examination, ECG, and urinalysis collected within 7 days of Cycle 1 Day 1 (C1D1) do not need to be repeated. The following will be performed according to the Schedule of Assessments ([Table 2](#)).

- Patient signature and date on current Institutional Review Board (IRB)-approved informed consent form - Prior to undergoing any study-specific procedure, patients must read, sign, and date the current IRB)-approved informed consent form. Patients may sign consent prior to the 28-day screening period.
- Medical history, baseline signs and symptoms, drug allergies, primary diagnosis, and demographics
- Physical examination, including examination of all major body systems, ECOG performance status, and vital signs - The patient's height will be obtained only at this Screening visit.

- Hematology, coagulation (prothrombin time and INR), and serum chemistry (including liver function tests and TSH) to be performed locally
- Hepatitis B and C serology will be done for all patients.
- Urinalysis to be performed locally - Microscopic analysis and/or urine protein-creatinine ratio (UPCR) should be performed as clinically indicated.
- CT or MRI scans of abdomen and pelvis to rule out metastatic disease. (within 3 months)
- Bone scans are to be performed if metastases to bone are suspected at screening (within 3 months) and to rule out bone metastases.
- Single tracing 12-Lead ECG (QT, PR, and QRS intervals and heart rate will be captured)
- Assessment of concomitant medications and treatments from 28 days prior to the start of study treatment
- Pre-operative baseline core tumor biopsy - Archival Tumor Tissue Specimens: Archival specimens (formalin-fixed, paraffin-embedded) of the primary cancer specimen for each study participant. It is preferable that the entire paraffin block be submitted, but if this is not feasible, then at least 20 unstained slides are requested for immunohistochemical and molecular analysis (sections of ~ 5 microns are preferred).

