5. SELECTION AND WITHDRAWAL OF PATIENTS

5.1. Patient Inclusion Criteria

1. Histologically confirmed (core biopsy proven) adenocarcinoma of prostate, localized high-risk or locally advanced
2. One of the below:
 - Gleason 7-8, any T-stage, and PSA > 20,
 - Gleason 8, \geq T2, any PSA,
 - Gleason 9-10, any T-stage, any PSA.
 - T3, any Gleason, any PSA
 - Subjects with positive pelvic lymph node(s) are eligible
3. Available biopsy of primary tumor or resected tumor specimen with adequate samples.
4. Prior treatment with systemic anti-cancer agents is not allowed.
5. ECOG PS = 0 or 1
6. Must have at least 1 target lesion
7. Life expectancy > 6 months
8. Adequate hematologic and end-organ function
 - ANC \geq 1500/mm³
 - Platelet count \geq 100,000/mm³
 - Hb \geq 8g/dl
 - Creatinine \leq ULN or Creatinine Clearance (CrCl) \geq 60 ml/min
 - Total Bilirubin \leq 1.5 x ULN (except subjects with Gilbert syndrome, who can have total Bilirubin < 2.x ULN and direct bilirubin within normal limits are permitted)
 - AST and ALT \leq 3.0 x ULN
9. Agreement to remain abstinent or use appropriate contraception.
10. Willingness and ability to consent for self to participate in study.
11. Willingness and ability to comply with scheduled visits, treatment plan, laboratory tests, and other study procedures.

5.2. Exclusion Criteria:

1. Prior treatment with CDK 4/6 inhibitor.
2. Prior treatment with systemic or radiation treatment for the primary cancer.
3. Major surgical procedure or significant traumatic injury within 4 weeks prior to study treatment, and must have fully recovered from any such procedure.
4. Personal history of any of the following conditions: syncope of cardiovascular etiology, ventricular arrhythmia of pathological origin (including, but not limited to, ventricular tachycardia and ventricular fibrillation), or sudden cardiac arrest.
5. Angina, myocardial infarction (MI), symptomatic congestive heart failure, cerebrovascular accident, transient ischemic attack TIA), arterial embolism,

pulmonary embolism, percutaneous transluminal coronary angioplasty (PTCA), or coronary artery bypass grafting (CABG) within 6 months prior to study treatment.

6. Known active viral or non-viral hepatitis or cirrhosis.
7. Any active infection requiring systemic treatment, positive tests for Hepatitis B surface antigen or Hepatitis C ribonucleic acid (RNA).
8. Known history of AIDS (acquired immunodeficiency syndrome)- defining illness.

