10. STATISTICS

10.1. Statistical Design/Sample Size

Simon's optimal two-stage design (Simon, 1989) will be used for conducting the trial. The null hypothesis is that the proportion of patients with PSA <0.5 without treatment is 5%, and the alternative hypothesis is that the proportion of patients with PSA <0.5 at 6 weeks into treatment is 30% or higher. The trial is carried out in two stages. In stage I, a total number of 5 patients is accrued. If there are 0 response (PSA < 0.5) among these 5 patients, the study will be early stopped. Otherwise, additional 18 patients will be accrued in stage II, resulting in a total number sample size of 23. If there are 4 or more responses (PSA < 0.5) among these 23 patients, we reject the null hypothesis and claim that the treatment is promising. The design controls the type I error rate at one-sided 0.025 and yields the power of 80%. If we reject the null hypothesis, seven additional patients will be enrolled to explore the association between biomarkers and clinical activities. To account for 10% screen failure, total 33 patients will be recruited to the study.

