10.1.1. Definition of Analyzed Study Populations

The following study populations will be considered when reporting study results:

- The study population for safety includes all patients receiving at least a portion of 1 dose of study drug (Abemaciclib).
- The study population for efficacy will include all safety population patients who have baseline and follow-up tumor measurements as required for assessment by iRECIST.

Only those patients who are deemed ineligible (e.g., do not satisfy eligibility criteria) or who receive no study drug (i.e., no Abemaciclib) will be eliminated from the analysis. Ineligible patients who receive therapy will not be included in the assessment of efficacy endpoints, but their data will be included in the assessment of all AE reporting.

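### Inclusion 6 asks for a target lesion without defining it; the reading chosen can change who is eligible and who counts toward the PSA decision, and no primary or secondary endpoint needs it.

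*Combined protocol and SAP*

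**What the plan says.** Section 5.1, item 6, and the same item in the synopsis: "Must have at least 1 target lesion". No size, site, imaging method or reference standard is attached to it.

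The neighbouring criteria select men in other ways. Item 1 asks for "Histologically confirmed (core biopsy proven) adenocarcinoma of prostate, localized high-risk or locally advanced". Item 2 works through Gleason score, T stage and PSA; one of its routes is "Gleason 9-10, any T-stage, any PSA". On nodes it says "Subjects with positive pelvic lymph node(s) are eligible", so nodal disease is allowed but not required.

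Section 4.1.2.1 orders "CT or MRI scans of abdomen and pelvis to rule out metastatic disease". Footnote f of the Schedule of Assessments repeats the scan only when PSA rises.

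Section 10.1 sets a two-stage design: stop if none of the first 5 men responds, otherwise continue to 23 and reject the null hypothesis at 4 or more responses. On recruitment it adds: "To account for 10% screen failure, total 33 patients will be recruited to the study".

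Section 10.1.1 limits the efficacy population to treated patients with baseline and follow-up tumor measurements for iRECIST, and then states: "Ineligible patients who receive therapy will not be included in the assessment of efficacy endpoints".

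**The concern.** In response-criteria language a target lesion is one chosen at baseline for measurement on imaging. Section 10.1.1 names iRECIST, and the abbreviation list carries its response categories, so a coordinator or auditor could reasonably apply that sense. The criterion then fits poorly with the rest of the plan. A man can satisfy items 1 and 2 with no imaging measurement, screening scans are ordered to exclude metastases, and no screening step selects or measures a lesion.

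Two things are at stake. The first is who enters: a strict reading narrows the population for no gain to a PSA endpoint. The second is who counts. A man enrolled under a lenient reading and later judged ineligible under a strict one leaves the efficacy analysis by the last sentence of 10.1.1. The trial is open-label with a single arm, so that judgement could be made after his PSA course is known.

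**Working it through.** **Which readings does the text allow?**

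- *iRECIST lesion.* For: Section 10.1.1, the abbreviation list, and Section 4.1.3, which refers to radiographic tumor assessment for men who stop treatment without progression. Against: entry by Gleason, T stage and PSA, optional nodes, scans only to rule out metastases, and response and progression assessed by PSA.
- *MRI-targeted intraprostatic lesion.* For: Section 2.6.1 expects every patient to have had an MRI-US guided biopsy at diagnosis, Section 9.1.2 describes targeted biopsy of dominant intraprostatic lesions, and the exploratory objectives include pre-treatment MRI-US imaging. Against: that MRI is not in the screening list or the Schedule of Assessments, and item 3 also accepts a resected specimen.

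**Does an endpoint need it?** The primary endpoint is a PSA nadir. The secondary endpoints are PSA decline before radiotherapy, time to PSA failure, and tolerability and feasibility. None uses lesion size. Only the exploratory imaging and tissue work could.

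**How many men would fail item 6?** This cannot be computed. Let f be the share of otherwise eligible men with a qualifying lesion; the document gives no value. Enrolling 30 needs 30/f such men:

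- f = 1.0: 30
- f = 0.8: 30/0.8 = 37.5, so 38
- f = 0.5: 30/0.5 = 60

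The plan recruits 33 (30 × 1.10), allowing for screen failure from all causes.

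**What does losing evaluable men do to the test?** Inputs from Section 10.1: response rate 5% under the null and 30% under the alternative, 5 men then 23 in total, stop at 0 of the first group, reject at 4 or more. With n1 men in stage I and n in total,

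P(reject) = Σ over x = 1 to n1 of P(Bin(n1, p) = x) × P(Bin(n − n1, p) ≥ 4 − x).

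*The plan's own design (5, 23):*

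- At p = 0.30, the terms for x = 1 to 5 are 0.3386 + 0.3043 + 0.1321 + 0.0283 + 0.0024, which sum to a power of 0.806 (computed before rounding the terms).
- At p = 0.05 the sum is 0.0174.
- Both agree with the stated 80% and one-sided 0.025.

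*Illustration (4, 18):* one stage I man and four later men are judged ineligible and not replaced, and the rule is unchanged.

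- At p = 0.30: 0.3454 + 0.2520 + 0.0751 + 0.0081 = 0.681.
- At p = 0.05 the sum is 0.0075.
- The chance of stopping after stage I when the true rate is 30% rises from 0.7^5 = 0.168 to 0.7^4 = 0.240.

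The error runs toward missing an active treatment; the false-positive rate falls.

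**The case against.** The best defence is that the term has a sensible local meaning. Men are expected to arrive with an MRI-US guided biopsy, and the lesion that biopsy targeted is a target lesion in everyday urological usage. The diagnostic work-up would normally document it, so it does not matter that the screening scan may be CT. This is one centre, Section 5.5 has eligibility settled before registration, and a single written definition would end the ambiguity. All of that is plausible and stands. It is not proven, because the supporting sentence sits in the risk section and is not an entry requirement.

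A second objection concerns the source of the loss. The iRECIST clause in 10.1.1 already puts men without measurements outside the efficacy set, so part of any shortfall belongs to that clause. This is also right. However, the sentence on ineligible patients acts separately: with the iRECIST clause repaired and item 6 left alone, a strict reading of item 6 would still remove men.

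A reader might go further and infer that item 6 bars most of the intended men, or turns this into a trial of men with enlarged pelvic nodes. The document does not support that. It gives no share of men with measurable lesions and does not say whether the prostate primary may serve as a target lesion. Barring most would need f below 0.5.

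**Conclusion.** The point holds as an undefined entry criterion with a real consequence for the analysis. Under the iRECIST reading it may exclude an unquantified share of the stated population; under the intraprostatic reading, perhaps few. Neither reading serves a primary or secondary endpoint.

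The stated sample size and error rates are reproduced and need no change. The power figure of 0.68 against 0.81 shows how sensitive the fixed rule is; it does not predict a loss. It assumes that 18 of 23 men remain evaluable, 4 of them in stage I, that nobody is replaced (the plan describes no replacement of treated ineligible men), and that 4 responses are still required.

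**What to change.** Delete item 6 from the synopsis and from Section 5.1. If the MRI-US and biopsy work needs a lesion, define an exploratory imaging and biopsy set and require, for that set only, at least one intraprostatic lesion visible on the diagnostic MRI. In the same amendment, remove the iRECIST measurement requirement from the efficacy population in Section 10.1.1; otherwise the same restriction remains in the analysis after it has gone from entry.

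The cost is a one-line deletion in two places, one sentence changed in 10.1.1 and, if wanted, a short definition of the exploratory set. The design of 5 then 23, with rejection at 4, stays as it is. The downside is that a few men without an MRI-visible lesion will not contribute to the exploratory imaging comparison.

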5.3. Patient Withdrawal Criteria

A patient should be withdrawn from study treatment if, in the opinion of the Investigator, it is medically necessary, or if it is the wish of the patient. If a patient does not return for a scheduled visit, every effort should be made to contact the patient. In any circumstance, every effort should be made to document patient outcome. Data to be collected at the end of study visit are described in the Schedule of Assessments ([Table 2](#)). Patients will be followed for at least 28 days after the last dose of study drug (Abemaciclib or ADT) for AEs. If the patient withdraws consent, no further evaluations should be performed, and no attempts should be made to collect additional data. In addition, patients will be withdrawn from treatment in the case of:

1. Lost to follow-up or noncompliant with the protocol
2. Any Abemaciclib dose delay > 7 days during the first cycle
3. Arterial thrombosis of any grade (including cerebrovascular ischemia, cardiac ischemia/infarction, or peripheral or visceral arterial ischemia) or Grade 3 or 4 venous thrombosis (including pulmonary embolism)

5.4. General Guidelines

Eligible patients will be entered on study at Kirklin clinic, UAB Hospital and Acton Road clinic. Site clinical research coordinator (CRC) will ensure study agent availability before enrolling patients. Following enrollment and registration by site CRC, patients should begin protocol treatment within 28 days. Issues that would cause treatment delays should be discussed with the Principal Investigator. If a patient does not receive protocol therapy following registration, the patient's registration on the study may be cancelled. The Study Monitor should be notified of cancellations as soon as possible.

5.5. Registration Process

The Clinical Trials Network Monitoring Office (CTNMO) of the UAB Comprehensive Cancer Center (CCC) coordinates investigator-initiated clinical trials under Good Clinical Practice conditions at UAB to achieve timely study subject enrolment. Once a study subject has been screened and deemed eligible for study entry by the site CRC, a study-specific number is assigned to the study subject and a Registration Form is completed. Queries regarding data accuracy are forwarded from the CTNMO to the site CRC for clarification or correction.

6. TREATMENT OF PATIENTS

6.1. Description of Abemaciclib Study Drug

[figure not shown]
Abemaciclib is an oral, selective, and potent ATP-competitive inhibitor of cyclin-dependent kinases 4 and 6 (CDK4 and CDK6, respectively). CDK4 and CDK6 promote cell growth by facilitating the progression of cells from the G1 to the S-phase of the mammalian cell cycle. This promotion of cell growth occurs primarily by counteracting the effects of a growth suppressor protein known as the retinoblastoma (Rb) protein, whereby the reversal of Rb mediated suppression is achieved by the phosphorylation of this protein by CDK4 and/or CDK6.

The CDK4/CDK6-Rb pathway is commonly altered in cancer cells, whereby the activation of this pathway contributes to enhanced growth. Accordingly in cancer cells, abemaciclib inhibits CDK4/CDK6-dependent phosphorylation of Rb, which subsequently blocks proliferation by inhibiting the progression of these cells from the G1 phase into the S and G2/M phases of the cell cycle.

Abemaciclib showed antitumor activity within multiple preclinical pharmacology models and an acceptable toxicity profile in nonclinical species. Abemaciclib has been shown to significantly inhibit tumor growth in multiple murine xenograft models for human cancer.

6.1.1. Abemaciclib Composition

The chemical name of Abemaciclib is (2-Pyrimidinamine, N-[5-[(4-ethyl-1-piperazinyl)methyl]-2-pyridinyl]-5-fluoro-4-[4-fluoro-2-methyl-1-(1-ethyl-1Hbenzimidazol-6-yl)-N-(5-((4-ethylpiperazin-1-yl)methyl)pyridin-2-yl)-5-fluoro-4-(4-fluoro-1-isopropyl-2-methyl-1H-benzo[d]imidazol-6-yl)pyrimidin-2-amine and the structural formula is presented in [Figure 2](#). Abemaciclib has a molecular formula of C₂₇H₃₂F₂N₈ and a molecular weight of 506.60.

Structure of abemaciclib.

6.1.2. Abemaciclib Dose Levels

Subjects in this phase II study will receive 150 mg BID PO dose of Abemaciclib. There will be no intra-patient dose escalation of Abemaciclib

6.1.3. Abemaciclib Packaging and Labelling

Abemaciclib will be provided by Lilly. Clinical trial materials will be labeled according to the country's regulatory requirements.

6.1.4. Abemaciclib Administration

Abemaciclib will be administered at a dose of 150 mg twice daily and it is provided as 50-mg tablets. Abemaciclib should be taken twice daily (with at least 6-hour separating doses) at the same time each day with a glass of water. Patients should be instructed to swallow tablets whole and not open, chew, or crush.

Doses of Abemaciclib will be self-administered except on the days scheduled to be given at the study clinic. Abemaciclib will be given daily in combination with ADT as long as subjects do not have toxicity, disease progression, have not met any criteria for study withdrawal or up to a maximum of 24 months. Intrasubject dose escalation of Abemaciclib is not permitted.

Table 3: Ideal Dosing Schema for Study Drugs and Abemaciclib Premedications

Sequence	Drugs	C1D1 and onwards
1	Abemaciclib PO (BID)	150 mg

6.1.5. Abemaciclib Dose Modification/Dose Delays

6.1.5.1. Rationale for Dose modifications

Modifications to Abemaciclib dose regimens are planned and independent of the determination of tolerability during the study, subjects may require modification of Abemaciclib if necessitated by drug-related or unrelated AEs.

6.1.6. Abemaciclib Drug Accountability

The Investigator must maintain an accurate accounting of Abemaciclib supplies. During the study, the following information must be recorded:

- Date of receipt, quantity, and lot number of the Abemaciclib study drug received.
- Identification number of the patient to whom the product is dispensed.
- The date(s) and quantity of the product dispensed.
- Dates and quantity of product returned, lost, or accidentally or deliberately destroyed.

Investigational Drug Accountability Logs should be maintained by the site and must be readily available for inspection.

6.1.7. Abemaciclib Study Drug Handling and Disposal

The Investigator must maintain an accurate accounting of the Abemaciclib product that is used. During the study, the following information must be maintained:

- Identification number of the patient to whom the product is dispensed.
- Lot number dispensed.
- The date(s) and quantity of the product dispensed.

6.2. Description of Androgen Deprivation Therapy

The commonly used preparations are listed below. However any of the other preparations with FDA approval, that result in androgen suppression are acceptable.

Goserelin acetate implant (Zoladex®) / Leuprolide (Lupron)

a. PHARMACOLOGY

Mechanism of Action: Following initial administration in males, goserelin causes an initial increase in serum luteinizing hormone (LH) and follicle stimulating hormone (FSH) levels with subsequent increases in serum levels of testosterone. Chronic administration of goserelin leads to sustained suppression of pituitary gonadotropins, and serum levels of testosterone consequently fall into the range normally seen in surgically castrated men approximately 2-4 weeks after initiation of therapy.

b. PHARMACOKINETICS

1. Absorption: Goserelin 3.6 mg is released slowly in first 8 days, and then rapid and continuous release for the remainder of the 28 day dosing period. Time to peak concentration for goserelin 3.6 mg is 12-15 days in males and 8-22 days in females. Goserelin 10.8 mg exhibits an initial rapid release resulting in a peak concentration at 2 hours after dosing.

From Day 4 until the end of the 12-week dosing interval, the sustained release of goserelin produces a reasonably stable systemic exposure.

2. Distribution: Apparent volumes of distribution determined after subcutaneous administration of 250 mcg aqueous solution of goserelin were 44.1 and 20.3 liters for males and females, respectively. Goserelin is approximately 27% protein bound.

3. Metabolism: Metabolism of goserelin by hydrolysis of the C-terminal amino acids is the major clearance mechanism. The half-life elimination ($t_{1/2}$) is approximately 4 hours in males and 2 hours in females

4. Elimination: Clearance of goserelin is very rapid and occurs primarily via urinary excretion (>90%; 20% as unchanged drug).

c. ADVERSE EFFECTS

1. Refer to the package insert or manufacturer website for the most complete and up to date information on contraindications, warnings and precautions, and adverse reactions.

Side Effects

Adverse events associated with the use of Leuprolide/Goserelin may include, but are not limited

to, the following:

- hot flashes

- injection site reactions
- weight gain
- increase in liver enzymes
- tiredness
- hypertension
- back and joint pain
- chills
- urinary tract infection
- decreased sex drive and trouble with erectile function

Adverse effects occurring in <1%, postmarketing, and/or case reports:

1. ALT increased, anaphylaxis, AST increased, diabetes, glucose tolerance decreased, hypercalcemia, hypercholesterolemia, hyperlipidemia, hypersensitivity reactions, hypotension, ovarian cyst, pituitary apoplexy, psychotic disorders, urticaria.
2. Pregnancy and Lactation: Not applicable as this study only enrolls male patients. Pregnancy category X in patients with endometriosis and endometrial thinning. Pregnancy category D in patients with advanced breast cancer. It is not known if goserelin is excreted in human milk, however goserelin is excreted in the milk of lactating rats.
3. Drug Interactions: Luteinizing hormone-releasing hormone analogs may diminish the therapeutic effect of antidiabetic agents. No formal drug-drug interaction studies have been performed. Please refer to the current FDA-approved package insert for additional information.
4. The FDA issued a safety communication in October 2010 based on their ongoing safety review of LHRH agonists. The safety communication discusses the potential for an increased risk of diabetes and cardiovascular disease (myocardial infarction, sudden cardiac death, stroke) associated with these agents. The risk is thought to be low in men receiving LHRH agonists for prostate cancer. In this trial, LHRH agonists are being administered for a short period of time. FDA recommendations include management of cardiovascular risk factors according to current standards of practice.

d. DOSING & ADMINISTRATION

1. Dosing – See Package Insert of preparation used.
2. Goserelin is administered subcutaneously into the anterior abdominal wall below the navel line using aseptic technique.

e. STORAGE & STABILITY

Refer to the current FDA-approved package insert for storage, stability and special handling information.

f. HOW SUPPLIED

1. Goserelin acetate implant is available in a 10.8 mg disposable syringe device. The unit is sterile and comes in a sealed, light- and moisture-proof, aluminum foil laminate pouch containing a desiccant capsule.
2. Goserelin is commercially available and will not be supplied. Refer to the current FDA-approved package insert for additional information.

Leuprolide (Eligard®, Lupron Depot®) (NSC-377526)

a. PHARMACOLOGY

Mechanism of Action: Leuprolide inhibits gonadotropin secretion by acting as an luteinizing hormone-releasing hormone (LHRH) agonist. Continuous administration results in

suppression of ovarian and testicular steroidogenesis due to decreased levels of LH and FSH with subsequent decrease in testosterone (male) and estrogen (female) levels. In males, testosterone levels are reduced to below castrate levels. Leuprolide may also act directly on the testes as well as act by a different mechanism not directly related to reduction in serum testosterone.

d. DOSING & ADMINISTRATION

1. Dosing – Per package insert. Typically 22.5 mg every 3 months
2. Leuprolide is administered intramuscular (Lupron Depot®) or subcutaneous (Eligard®) injection based on commercial depot formulation. Injection sites should be varied periodically.

e. STORAGE & STABILITY

Refer to the current FDA-approved package insert for storage, stability and special handling information.

f. HOW SUPPLIED

1. Leuprolide acetate is available in 3.75 mg, 7.5 mg, 11.25 mg, 22.5 mg, 30mg, or 45 mg depot formulation kit with accompanying diluent. The prefilled dual chamber syringe contains lyophilized microspheres of leuprolide acetate incorporated in a biodegradable lactic acid polymer.
2. Leuprolide/Goserelin is commercially available and will not be supplied.

Other LHRH agents can be utilized per the FDA approved dose and schedule. GNRH antagonists cannot be used.

